4.2. Handling of missing data

Patients with major deviation to the protocol, i.e. lack of ultrasound imaging data, will not be analyzed.

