2 PROJECT OBJECTIVES AND DESIGN

2.1 Primary objective

The primary objective of the research is to evaluate the ultrasound image quality for arrhythmia patients, to investigate potential echogenicity and artefact issues, which may arise from age, body composition, mechanical valves, leads from implanted devices, etc. in order to have a representative sample of the variety of ventricular tachycardia patients.

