2.2 Primary and additional endpoints

Objectives

The primary research objective is the proportion of subjects who have a positive evaluation in image interpretation metric and positive visual inspection of the ultrasound images.

Secondary objective; Additionally, for patients for whom a full field of view CT scan is available, the theoretical impact of probe positioning during a CT scan is analysed for hypothetical treatment planning.

Endpoints

Primary

The objective will be quantitatively assessed by scoring each patient as follows:

- A) Cardiac motion analysis performance:
 - o Score 1 if analysis of the ultrasound images with the EBAMed software gives a cardiac phase error (within R-R interval) < 0.1
 - o Score 0 otherwise
- B) Respiratory motion analysis performance:
 - o Score 1 if analysis of the ultrasound images with the EBAMed software gives a motion amplitude lower than 30 mm and if the number of breathing cycles matches the one observed from the motion of the chest.
 - o Score 0 otherwise

- C) Image quality performance:
 - o Score 1 if visual inspection by a member of San Matteo team can identify in the ultrasound images at least one of these structures: left ventricular wall, interventricular septum, or heart valve.
 - o Score 0 otherwise
- D) Image quality performance :
 - o Score 0 if visual inspection by a member of San Matteo team identifies that the heart becomes invisible for part of the time due to tissue motion linked to respiration.
 - o Score 1 otherwise

For each patient, scoring will be done for each imaging view (parasternal and apical). If the score is 2 (at least 1 point in A or B and 1 point in C or D) or higher for at least one of the imaging views, the outcome will be considered as positive. The final result will be the proportion (in %) of patients with a positive outcome defined as the number of patients with a positive evaluation divided by the total number of patients x 100.

Secondary

The objective will be quantitatively assessed by scoring each patient (only those with a CT available):

- with Score 1: if a successful radio-ablation treatment plan respecting dose constraints can be created using a clinical treatment planning software (see details below) and,
- with Score 0: if it is not possible to create such a treatment plan .

The final result will be the proportion of patients (in %) with a 1 Score: number of patients with score 1 divided by the number of patients with Score 0 or 1 x 100.

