3.3 Study procedures

Patient's participation starts at informed consent signature and ends after completion of the study's Cardiac Motion Monitoring procedure.

The study will start as soon as the protocol is approved by ethics. The recruitment period is expected to last from May 2021 to August 2021.

The table below describes the data collection and study procedures:

Data Collection	Information and informed consent form	Procedure (within 30 days of consent)
Signature	X	
Demographics and cardiovascular history		X
Cardiac Motion Monitoring with Demonstrator 2		X
CTscan (if available)		(X)
Adverse Event		X
Deviations, technical issues		X

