3.4 Withdrawal and discontinuation

Patient will be withdrawn from the study if they do not pertain the enrollment criteria, or in case of absence of a Cardiac Motion monitoring procedure by the time the study ends.

Patients can withdraw their consent at any time. No additional data will be collected after patient withdrawal. As much as possible, the reason for patient withdrawal shall be collected.

In case of a patient withdrawal before any data is collected, a new enrollment may take place to ensure enough data is collected in the study.

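### Section 4.2 drops patients with no ultrasound images whatever the cause; a failed acquisition is a negative outcome under Section 2.2, so dropping it can only raise the primary proportion

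*Protocol*

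**What the plan says.** - **Section 4.2 (missing data):** "Patients with major deviation to the protocol, i.e. lack of ultrasound imaging data, will not be analyzed". This is the whole rule. Lack of images defines the deviation, and no cause is named.
- **Section 2.2 (primary endpoint):** each view is scored 0 or 1 on four items, A to D. A view counts as positive with a score of 2 or more, made up of "at least 1 point in A or B and 1 point in C or D", and one positive view is enough for the patient. The result is "the number of patients with a positive evaluation divided by the total number of patients x 100". Which total is meant is not said.
- **Section 2.1 (primary objective):** the study is to evaluate image quality and "to investigate potential echogenicity and artefact issues, which may arise from age, body composition, mechanical valves, leads from implanted devices".
- **Section 3.4 (withdrawal):** patients are already withdrawn "in case of absence of a Cardiac Motion monitoring procedure by the time the study ends". A new enrolment is foreseen only for a withdrawal before any data are collected.
- **Section 3.3 (schedule):** "Deviations, technical issues" are recorded at the procedure.
- **Section 4.1 (sample size and analysis):** 24 patients, an aim of 90% (22/24), and 95% confidence intervals for the proportion overall and by patient characteristics such as age and BMI.

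**The concern.** Section 3.4 already deals with patients who had no procedure. What Section 4.2 adds is therefore mainly patients whose procedure took place but left no images. That group can contain two different things: recordings lost for reasons unrelated to the patient, and patients in whom no image could be obtained. The first is ordinary missing data. The second is the outcome the study is meant to measure, in its most unfavourable form.

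Excluding both alike makes exclusion depend on the outcome. The bias has one direction only, towards a more favourable feasibility figure. The proportions by age and BMI group are exposed in the same way, in smaller groups, and Section 2.1 itself names age and body composition as possible causes of poor imaging.

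**Working it through.** **1. The plan's own figures.** Section 4.1 gives a lower 95% limit of 73% for 22/24 and 79% for 23/24. The exact (Clopper-Pearson) interval gives 73.0% and 78.9%, which matches both. Wilson (74.2%, 79.8%) and Agresti-Coull (73.0%, 78.1%) do not match both. Exact intervals are used below.

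**2. Score of a patient with no images in either view, from Section 2.2.**

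- A is 1 only if software analysis of the images "gives a cardiac phase error (within R-R interval) < 0.1", otherwise 0. Without images, A = 0.
- B is 1 only if the software gives a motion amplitude under 30 mm and a matching breath count, otherwise 0. Without images, B = 0.
- C is 1 only if a structure is identified in the images, otherwise 0. Without images, C = 0.
- D is 0 if the heart is seen to disappear with respiration, otherwise 1. Without images, D is 0, or 1 by default.

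The total is 0 or 1, below 2, and the required point in A or B is missing. The outcome is negative under either reading of D.

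**3. Effect of the exclusion.** Let s be the number of positive patients and k the number of attempted patients without images, out of 24.

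- As written in Section 4.2: s/(24 − k)
- Counted as negative: s/24
- Ratio: 24/(24 − k)
- Difference: s·k / [24(24 − k)], which is never below zero and is above zero whenever s and k are

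**4. Numbers.** The Protocol gives no rate of failed acquisition, so k = 0 to 4 is an assumption. The values of s are chosen near the 90% aim.

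| k | Ratio | As written (exact 95% CI) | Counted as negative (exact 95% CI) |
|---|---|---|---|
| 0 | 1.00 | 22/24 = 91.7% (73.0–99.0) | the same |
| 1 | 1.04 | 21/23 = 91.3% (72.0–98.9) | 21/24 = 87.5% (67.6–97.3) |
| 2 | 1.09 | 20/22 = 90.9% (70.8–98.9) | 20/24 = 83.3% (62.6–95.3) |
| 3 | 1.14 | 19/21 = 90.5% (69.6–98.8) | 19/24 = 79.2% (57.8–92.9) |
| 4 | 1.20 | 18/20 = 90.0% (68.3–98.8) | 18/24 = 75.0% (53.3–90.2) |

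**5. How often the 90% aim is crossed.** The as-written figure reaches 90% while the other does not for these s: k = 1, only 21; k = 2, 20 or 21; k = 3, 19 to 21; k = 4, 18 to 20. With k = 1, both figures miss the aim at s = 20 (20/23 = 87.0%, 20/24 = 83.3%) and both meet it at s = 22 (22/23 = 95.7%, 22/24 = 91.7%).

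**The case against.** The strongest reply is that Section 4.2 speaks of a major deviation. That word suggests a departure from the planned procedure, such as a recording not made or lost, and not a correctly performed examination in a patient with a poor acoustic window. On that reading the harmful case falls outside the rule. But the sentence equates the deviation with lack of imaging data and names no cause, so as written it covers both.

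Second, the group may be almost empty. Section 3.1.2 sets timed recordings with no image-quality condition for starting, and lets the probe be held by hand for the parasternal view. Poor echogenicity should then usually give poor recorded images, which stay in and score as they deserve. A patient with images in one view is also unaffected. This stands: the bias needs an attempt with no images in either view, and it is zero if none occurs.

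Third, the items in Section 2.2 presuppose images, so calling such a patient negative is an inference. It relies on the default score of 0 for A, B and C. Those defaults are written without exception, and the result does not depend on D.

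Fourth, Sections 2.2 and 4.2 can be read together, with the total meaning the analysed patients. That removes a formal contradiction but leaves the bias.

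Finally, k is hypothetical, crossing 90% triggers no decision, and the intervals are wide: for 22/24, 99.0 − 73.0 = 26 points. All of this is true and limits how serious the point is.

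**Conclusion.** The concern holds, and the rule should be changed. The direction of the bias is certain: excluding attempted acquisitions without images can only raise the primary proportion, or leave it unchanged when there are none or no successes. The size is not known. Near the 90% aim, one such patient adds about 4 points (91.3 − 87.5 = 3.8) and two add about 8 (90.9 − 83.3 = 7.6).

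This rests on two things: that some procedures are started but give no images in either view, for which the Protocol offers no rate, and that the default scores in Section 2.2 apply to them. Recording or storage loss fits the wording of Section 4.2 as well, and the Protocol does not say which cause would be more common. What is at stake is an over-favourable feasibility estimate, not a wrong formal decision.

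**What to change.** Replace the sentence in Section 4.2 with:

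> All patients in whom the Cardiac Motion Monitoring procedure was started are analysed for the primary endpoint. A patient in whom no ultrasound images could be obtained in either view counts as a negative outcome; a patient with images in one view only is judged on that view. Excluded are only patients whose procedure was never started, or whose data were lost for a documented reason unrelated to imaging (for example an equipment or storage fault, or consent withdrawal). These are listed with reasons, and a sensitivity result counts as negative those whose procedure was started.

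In Section 2.2, define the denominator as this set. The scoring of A to D does not change.

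Whether an equipment fault is truly unrelated to imaging is partly a judgement when the equipment is itself a demonstrator. The list of reasons and the sensitivity result make that judgement visible.

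The cost is a short paragraph in place of one sentence, and a few words in Section 2.2. No new data are needed, because deviations and technical issues are already recorded at the procedure (Section 3.3). The one drawback is that the reported proportion may be somewhat lower.

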4.3 Core laboratory

The data will be shared with EBAMed SA to perform the analysis of the records upon their anonymization.

5 REGULATORY ASPECTS AND SAFETY

5.1 Local regulations / Declaration of Helsinki

This research project will be conducted in accordance with the protocol, the Declaration of Helsinki [3], the principles of Good Clinical Practice, and local relevant regulations. The Project Leader acknowledges his responsibilities as both the Project Leader and the Sponsor.

5.2 Notification of safety and protective measures

Although not expected, the project leader will promptly notify the Ethics Committee (within 24 hours) if immediate safety and protective measures have to be taken during the conduct of the research project.

5.3 Serious events

If a serious adverse event occurs, the research project will be interrupted, and the Ethics Committee notified on the circumstances.

5.4 Amendments

Substantial changes to the project set-up, the protocol and relevant project documents will be submitted to the Ethics Committee for approval before implementation. Exceptions are measures that have to be taken immediately in order to protect the participants.

5.5 End of project

Upon project completion or discontinuation, the Ethics Committee is notified within 90 days.

5.6 Insurance

For any damage caused by the trial, the IRCCS Policlinico San Matteo Foundation insurance policy is active to cover the civil liability of its employees.

6 BENEFIT-RISK ASSESSMENT

The study is set-up in order to minimize the burden on the patient, with a single non-invasive, short and simple Cardiac Motion monitoring procedure. The procedure bears no risk for the study participant. The participant will not get direct benefit from her/his participation in the study, but, as mentioned in *1 Background and project rationale*, the research has the potential to enable the creation of a medical device, that will eventually benefit patients with ventricular tachycardia and other cardiac pathologies in the future.

7 QUALITY CONTROL DATA PROTECTION

7.1 Quality measures

Data will be collected on site and maintained in dedicated study files. Training and support will be provided by EBAMed SA on the use of the system (Demonstrator 2 and related components).

For quality assurance the Ethics Committee may visit the research sites. Direct access to the source data and all project related files and documents must be granted on such occasions.

7.2 Data recording and source data

The source data is collected on paper Case Report Forms (CRF) and retained at study site. Any error or correction will be marked in a legible format, with initials and date of input by the corrector. CRF data is transferred to electronic format in a single database for further analysis. The Demonstrator 2 system session records are saved on the Workstation in electronic format. Demonstrator 2 system data is saved in an external hard drive for archiving.

7.3 Confidentiality and coding

Study data will be handled with uttermost discretion and is only accessible to authorized personnel who require the data to fulfil their duties within the scope of the research project. On the CRFs and other study specific documents, participants are only identified by a unique participant number.

7.4 Retention of study data

The source data will be maintained at the site and stored for a minimum of 5 years. The data may be pooled with additional future studies of similar interest to increase study power.

8 FUNDING / PUBLICATION / DECLARATION OF INTEREST

The site receives funding by EBAMed to undertake the study. The site and EBAMed have a contract in place that covers study data sharing.

The investigators have no personal interest, financial or otherwise, in the conduct of the study.

In the event of a publication, both the study leader, the study team and EBAMed will collectively participate.

10 APPENDIX

Appendix A - Demonstrator IFU

IFU_2021MAR23_OperationManualDemonstrator2IOCabinet_v1.0

Appendix B – ECG Operator’s Guide

Accusync42_OperatorGuide

Appendix C - Optical Localization System User Guide

20200811_EXP_HWB_NDI-PolarisVega-User-Guide
